10.3.4 Handling of patients after permanent treatment discontinuation (SoC or IMP)

- All definitive discontinuation of study treatment should be recorded by the Investigator in the appropriate screens of the e-CRF and in the patient's medical records when considered as confirmed. The registration center should be notified when a patient prematurely discontinues the study. Patients should be asked to stick to the visit schedule for measuring laboratory test values until the end of study (Week 36).
- When patients permanently discontinue the study (regardless of the reasons) before Week 24 (6 months), they will have an unscheduled on-site visit as soon as possible (preferably within 7 days from treatment discontinuation) with assessments originally planned at the EOT visit (Week 36).
- When patients in the alirocumab arm permanently discontinue the study (regardless of the reasons) on Week 24 (6 months) or after, the Investigator should make the best effort to schedule the evaluation IVUS imaging with assessments originally planned at the EOT visit (Week 36) within 2 weeks from the last IMP administration (the earliest last IMP administration occurs on Week 22). If the patients decline the evaluation IVUS imaging after the study discontinuation, they will have an unscheduled on-site visit as soon as possible (preferably within 7 days from treatment discontinuation) with assessments originally planned at the EOT visit (Week 36).
- When patients in the SoC arm permanently discontinue the study (regardless of the reasons) on Week 24 (6 months) or after, the Investigator should make the best effort to

schedule the evaluation IVUS imaging with assessments originally planned at the EOT visit (Week 36) within 2 weeks from the determination date of the study discontinuation. If the patients decline the evaluation IVUS imaging after the study discontinuation, they will have an unscheduled on-site visit as soon as possible (preferably within 7 days from treatment discontinuation) with assessments originally planned at the EOT visit (Week 36).

- When patients, who develop AEs including AESIs and/or SAEs and need to be followed up as specified in this protocol, permanently discontinue the study, they will be followed up until recovery or stabilization of the AEs.

Note: If the evaluation IVUS imaging cannot be performed within 2 weeks from the last Praluent® administration in the alirocumab arm or 2 weeks after the day when the study discontinuation is determined in the SoC arm, lipid values measured at the study site should be recorded at the evaluation IVUS imaging.

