
5 STUDY OBJECTIVES

5.1 PRIMARY

To compare the effect of Praluent® with SoC on coronary atheroma progression (percent change in normalized TAV) after 9 months of treatment in patients who had ACS within 4 weeks prior to randomization, with hypercholesterolemia treated with any statin.

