10.1.1.1.4 Study Site Visit 4 (Week 24 / D169 ± 7 days)

This visit includes:

- On-site visit.
- EQ-5D patient questionnaire.
- IMP/NIMP compliance check including diet therapy (Patients should be on a diet following JAS guideline or equivalent).
- Body weight.
- Vital signs: heart rate and sitting SBP and DBP.
- Record of all concomitant medications including CV medications.
- Collection of adverse events including CV events (if any).
- Fasting blood sample listed below will be collected and measured.
 - Hematology and chemistry.
 - TC, calculated and directly measured LDL-C, HDL-C, TG, non-HDL-C (central laboratory).
 - HbA1c (central laboratory).

Note: Additional blood samples can be obtained for measurement of above listed items and others at the study site by Investigator's judgment as needed.

- When the Investigator or the site medical staff confirms all required measurements are completed, the patient in the alirocumab arm will receive Praluent® administration.
- The patient should be observed for at least 30 minutes after Praluent® administration.
- If patient is in the SoC arm, ongoing LMTs will be continued unless modification of LMTs is made by the Investigator's medical judgment.
- For the patient in the alirocumab arm, an appointment will be given for next Praluent® administration visit (Week 26 / D183).
- For the patient in the SoC arm, an appointment will be given for next phone-call interview (Week 28 / D197).
- The Investigator should make a schedule with the patient for the evaluation IVUS study at the EOT (Week 36 ± 2 weeks) by this on-site study visit if possible.

10.1.1.1.5 Study Site Visit 5 (End of Treatment Visit, Week 36 / D253 ± 14 days)

This study visit includes:

- On-site visit.

- Contact the registration center to document the end of study.

Note: If the evaluation IVUS imaging is completed in this visit, EOT will be the end of study. If the evaluation IVUS imaging is scheduled after this visit, the contact with the registration center will be made when the evaluation IVUS imaging has been completed and this point is considered the end of study.

- EQ-5D patient questionnaire.
- IMP/NIMP compliance check including diet therapy (Patients should be on a diet following JAS guideline or equivalent).
- Body weight.
- Vital signs: heart rate and sitting SBP and DBP.
- Record of all concomitant medications including CV medications.
- Collection of adverse events including CV events (if any).
- Urine pregnancy tests (WOCBP).

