## 1.6 STATISTICAL MODIFICATIONS MADE IN THE STATISTICAL ANALYSIS PLAN

The SAP version 1 was modified between the study start and database lock (DBL) for the main study in order to follow the last amended protocol, to address the further information on IVUS and optical coherence tomography (OCT) imaging analysis, to keep a consistency with the study objectives, and to correct erroneous descriptions. The changes in the SAP from version 1 to version 2 are as follows:

- **Section 2.3.1:** In the definition of mITT population, "Another one assessed during the efficacy treatment period and within the Week 36 analysis window", which is mentioned in the 3rd item of [Table 1](#) in [Section 1.7](#), was changed to "Another one assessed after 24 weeks of treatment ", since the statement in version 1 was inconsistent with the last amended protocol, and IVUS imaging outside the efficacy treatment period could not be considered as protocol deviation.
- **Section 2.3.1.1:** In the definition of PP population, the following criteria were changed:
  - "Patients with analyzed vessel length less than 10 mm" was added, since it is considered major deviation from IVUS imaging procedure and it may have an impact on IVUS parameters.
  - "LDL-C  $\geq$ 100 mg/dL" was changed to "LDL-C at patient selection  $\geq$ 100 mg/dL for patients enrolled based on the protocol amendment 1;  $\geq$ 70 mg/dL for patients enrolled based on the protocol amendment 2 or later" according to the amended protocol.
  - "Background therapy deviation" was removed, since the study team found that in the study protocol the use of background therapy including statin is eventually dependent upon the doctor and so deviation related to background therapy cannot be specified.
- Several analyses including substudy analyses for optical coherence tomography (OCT), additional efficacy analyses (Section 2.4.4.4) were removed, since they are beyond the study objectives.

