**Table 3 - Analysis windows definition**

Time point	Targeted study day	Analysis window in study days
Week 36	253	$\geq 169$

Study days are calculated from the day of randomization, the day of randomization being Day 1.

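### Protocol 10.3.4 leaves Week 24 undefined in study days and times the two arms' images differently, so an on-time IVUS after an early stop can fall before Day 169, where SAP Table 3 cannot use it

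*Protocol*

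**What the plan says.** **Timing of the image after a stop.** Protocol 10.3.4 has separate bullets for stops before Week 24 and for stops on Week 24 or after. The earlier-stop bullet asks for an unscheduled visit and does not name the IVUS. For later stops, "the Investigator should make the best effort to schedule the evaluation IVUS imaging with assessments originally planned at the EOT visit (Week 36". In the alirocumab arm this is due "within 2 weeks from the last IMP administration (the earliest last IMP administration occurs on Week 22". In SoC it is due "within 2 weeks from the determination date of the study discontinuation". The Note closing the section covers images that miss either limit: "lipid values measured at the study site should be recorded at the evaluation IVUS imaging". It sets no date for such an image.

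**What the analysis accepts.** SAP Table 3 (2.5.4.1) gives the Week 36 IVUS window as Day 169 or later, with no upper limit: "Study days are calculated from the day of randomization, the day of randomization being Day 1". The primary endpoint (SAP 2.1.3.1) needs an image after at least 24 weeks of treatment and inside that window. mITT membership (SAP 2.3.1.1) also needs an image after 24 weeks of treatment.

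**Visit windows.** The visit in question is "Study Site Visit 4 (Week 24 / D169 ± 7 days" (Protocol 10.1.1.1.4). The Week 22 injection is on Day 155, also with 7 days either side (Protocol 10.1.1.2).

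**The concern.** The imaging rule is written in visit weeks and in days since the last dose or decision. The analysis rule is written in study days from randomization. The two meet at a single nominal day, and both the Week 22 injection and the Week 24 visit may move by a week. Section 10.3.4 does not say whether a stop at a Week 24 visit held on, say, Day 163 is a stop on Week 24.

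If it is, a site can follow 10.3.4 and obtain an image that the primary analysis cannot use. The PP set is a subset of mITT, so it cannot use the image either. The patient has then had an invasive procedure, and the primary endpoint is still missing.

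The alirocumab anchor also looks backwards. The 2-week limit runs from the last injection, not from the event that triggers the image, so it can be partly or wholly spent when the stop is decided.

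**Working it through.** **Inputs.** Study day = 7 × week + 1, because randomization is Day 1. Week 22 = Day 155, Week 24 = Day 169, Week 36 = Day 253. Week 22 injection window: Days 148 to 162. Week 24 visit window: Days 162 to 176. Table 3 floor: Day 169.

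**Step 1: the plan's own figure.** Earliest last injection at Week 22: 155 + 14 = 169. The earliest nominal Week 24 stop is also Day 169. One day satisfies both rules, and it is inside the Table 3 window. On nominal dates nothing is discarded.

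**Step 2: a Week 24 visit held early counts as Week 24.** On-time days run from the stop to last dose + 14 in alirocumab, and from the stop to stop + 14 in SoC. Usable days are those from Day 169. With a nominal Day 155 dose:

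| Stop decided | Alirocumab on-time days | Usable | SoC on-time days | Usable |
|---|---|---|---|---|
| Day 162 | 162–169 (8) | 1 | 162–176 (15) | 8 |
| Day 163 | 163–169 (7) | 1 | 163–177 (15) | 9 |
| Day 168 | 168–169 (2) | 1 | 168–182 (15) | 14 |
| Day 169 | 169 (1) | 1 | 169–183 (15) | 15 |

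On-time images on Days 162 to 168 are possible in both arms. Alirocumab has one usable day in each row, and SoC has at least eight.

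**Step 3: the injection date moves within its window.** For a last dose on Day d and a stop by Day 169, the usable on-time days number d + 14 − 169 + 1 = d − 154, or zero if that is negative.

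- d = 148 to 154 (7 of the 15 permitted dose days): none. For example, 148 + 14 = 162.
- d = 155: one day.
- d = 162: eight days (169 to 176).

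If the stop is decided on Day 169 or later, a dose on Days 148 to 154 means that the limit has already lapsed.

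**Step 4: an earlier interruption.** Protocol 10.3.1 allows injections to be withheld temporarily. If the last dose was at Week 18 (Day 127) and the permanent stop is decided at Week 24, the limit ended on Day 127 + 14 = Day 141, 28 days before Day 169. The Week 22 parenthesis in 10.3.4 does not allow for this.

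**Step 5: scale, as illustration only.** The plan's 75 per arm reproduces: difference 8, SD 15 and two-sided 5% give a noncentrality of 8 / (15 × √(1/75 + 1/75)) = 3.27 and t-test power of 90.1%. If 2 alirocumab images were lost beyond the planned 25% (73 against 75), noncentrality is 3.24 and power 89.7%. If 5 were lost (70 against 75), it is 3.21 and 89.0%. The counts 2 and 5 are assumptions.

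**The case against.** The case that this needs little or no action is strong in several respects.

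- **The rule applies only from Week 24.** If Week 24 means Day 169, no image is triggered earlier. A Day 148 dose then leaves no on-time day; it does not produce an early image that is thrown away. This stands, so the early-image problem depends on reading Week 24 with its visit window. The protocol neither adopts nor excludes that reading.
- **A lapsed limit is provided for.** The instruction is best effort, the closing Note foresees later imaging, and Table 3 has no upper limit. SAP 1.6 says that "IVUS imaging outside the efficacy treatment period could not be considered as protocol deviation", so a late image stays in mITT. This stands. The remaining gap is that the Note gives no target date and no floor.
- **The affected group is narrow.** It is patients who stop around Week 24 or after a run of missed injections. The one related figure is in Protocol section 4: 4.9% of alirocumab patients in the Japanese phase 3 study stopped because of adverse events over 52 weeks. It covers only adverse-event stops but spans a full year.

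Three stronger inferences are tempting, and the documents do not support them.

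- **Only alirocumab images can be discarded.** On the reading that allows early images at all, SoC images can also fall on Days 162 to 168. The exposure differs in degree.
- **Analysing a Day 169 image as Week 36 is an error.** The objective is the change "after 9 months of treatment in patients who had ACS within 4 weeks prior to randomization", and Day 169 is 168/252 = 67% of the planned interval. But protocol and SAP both state the 24-week rule, apply it to both arms, and limit the PP analysis to images from Weeks 34 to 38. It is a pre-specified choice. The resulting dilution cannot be sized without a number of early stoppers and a time course of effect, and the documents give neither.
- **All stoppers should be imaged at Week 36 ± 2 weeks.** Protocol 6.1 and section 10 want imaging while the alirocumab effect remains, and waiting may lose patients. That is a trade-off, and nothing in the documents settles it.

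**Conclusion.** The point holds in a limited form. Section 10.3.4 and SAP Table 3 agree on nominal dates but are not tied together in study days. If the Week 24 visit window counts, on-time images on Days 162 to 168 are possible in both arms and cannot enter the primary analysis. The alirocumab arm is more exposed because its 2 weeks run from the last dose. Separately, the alirocumab limit can lapse before the stop is decided, after a Week 22 dose on Days 148 to 154 or an earlier interruption, and the Note then gives no date to aim for.

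Few patients are likely to be affected. The documents do not allow the number to be derived, and the illustrated power losses are under about 1 percentage point. The reason to act is that an invasive image should not be taken on a day when it cannot serve its purpose, and that preventing this costs almost nothing.

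**What to change.** In Protocol 10.3.4:

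1. Define Week 24 as Day 169, counted from randomization as Day 1.
2. State that the evaluation IVUS must not be taken before Day 169 in either arm, so that the instruction matches SAP Table 3.
3. Reconcile the two arms' timing anchors with each other and with the closing Note, including what date to aim for when the alirocumab limit has already passed.
4. Say which bullet covers a patient who stops at a Week 24 visit held on Days 162 to 168. Under a strict Day 169 definition that patient falls under the earlier-stop bullet, which does not name an IVUS.

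No SAP change is needed. The cost is a short wording amendment with no added procedure. For a patient who is imaged, the floor means waiting at most 7 days (Day 162 to Day 169). It gives up nothing in the primary analysis, because an image before Day 169 could not be used there.

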10.3.5 Procedure and consequence for patient withdrawal from study

The patients may withdraw from the study, before study completion if they decide to do so, at any time and irrespective of the reason.

If possible, the patients should be assessed using the usual scheduled procedure on the visit day of the end of study.

For patients who fail to return to the site, the Investigator/sub-Investigator should make the best effort to re-contact the patient (e.g., contacting patient's family or private physician, review available registries or health care database), and to determine his/her health status, including at least his/her vital status. Attempts to contact such patients must be documented in the patient's records (e.g., number of times and dates of attempted telephone contact, receipt for sending a registered letter).

Patients who have withdrawn from the study cannot be re-randomized (treated) in the study. Their patient number and treatment number must not be reused.

10.4 OBLIGATION OF THE INVESTIGATOR REGARDING SAFETY REPORTING

10.4.1 Definitions of adverse events

10.4.1.1 Adverse event

- An **adverse event** (AE) is any untoward medical occurrence in a patient or clinical investigation patient administered a pharmaceutical product and which does not necessarily have to have a causal relationship with this treatment.
- All AE diagnosed by the Investigator, irrespective of the results of the adjudication for CV events, will be reported and described.

- All AEs will be coded to “LLT”, “PT”, “HLT”, “HLGT”, and associated primary “SOC” using the version of MedDRA currently in effect at Sponsor or delegate at the time of the considered database lock.

10.4.1.2 Serious adverse event

A **serious adverse event** (SAE) is any untoward medical occurrence that at any dose:

- Results in death
- Life-threatening

Note: The term “life-threatening” in the definition of “serious” refers to an event in which the patient was at risk of death at the time of the event; it does not refer to an event which hypothetically might have caused death if it were more severe.

- Requires inpatient hospitalization or prolongation of existing hospitalization
- Results in persistent or significant disability/incapacity
- Congenital anomalies/birth defects, or
- Other medically important event

Medical and scientific judgment should be exercised in deciding whether expedited reporting is appropriate in other situations, such as important medical events that may not be immediately life-threatening or result in death or hospitalization but may jeopardize the patient or may require medical or surgical intervention (i.e., specific measures or corrective treatment) to prevent one of the other outcomes listed in the definition above.

Note: The following list of medically important events is intended to serve as a guideline for determining which condition has to be considered a medically important event. The list is not intended to be exhaustive:

- Intensive treatment in an emergency room or at home for:
 - Allergic bronchospasm,
 - Blood dyscrasias (i.e., agranulocytosis, aplastic anemia, bone marrow aplasia, myelodysplasia, pancytopenia, etc.),
 - Convulsions (seizures, epilepsy, epileptic fit, absence, etc.).
- Development of drug dependence or drug abuse.
- ALT >3 x upper limit of normal range (ULN) + total bilirubin >2 x ULN or asymptomatic ALT increase >10 x ULN.
- Suicide attempt or any event suggestive of suicidality.
- Syncope, loss of consciousness (except if documented as a consequence of blood sampling).
- Bullous cutaneous eruptions.

- Cancers diagnosed during the study.
- Chronic neurodegenerative diseases (newly diagnosed) or aggravated during the study.

10.4.1.3 Adverse event of special interest

An **adverse event of special interest** (AESI) is an AE (serious or non-serious) that need to be monitored, documented, and managed in a pre-specified manner described in the protocol. Please see [Section 10.4.6](#) and [Section 17](#), Appendix F for additional information.

10.4.2 General guidelines for reporting adverse events

All AEs, regardless of seriousness or relationship to study treatment, spanning from the signature of the informed consent form until the end of the study as defined by the protocol for that patient, are to be recorded on the corresponding page(s) or screen(s) of the e-CRF.

Whenever possible, diagnosis or single syndrome should be reported instead of symptoms. The Investigator/sub-Investigator should specify the date of onset, intensity, action taken with respect to study treatment, corrective treatment/therapy given, additional investigations performed, outcome, and his/her opinion as to whether there is a reasonable possibility that the AE was caused by the study treatment or by the study procedure(s).

The Investigator/sub-Investigator should take appropriate measures to follow all AEs until clinical recovery is complete and laboratory results have returned to normal, or until progression has been stabilized, or until death, in order to ensure the safety of the patients. This may imply that observations will continue beyond the last planned visit per protocol, and that additional investigations may be requested by the monitoring team up to as noticed by the Sponsor. When treatment is prematurely discontinued, the patient's observations will continue until the end of the study as defined by the protocol for that patient.

Laboratory and vital signs are recorded as AEs only if:

- Symptomatic and/or
- Requiring either corrective treatment or consultation, and/or
- Leading to study treatment discontinuation or modification of dosing, and/or
- Fulfilling a seriousness criterion, and/or
- Defined as an AESI

See [Section 17](#), Appendix F for summary of AE reporting guidelines.

10.4.3 Instructions for reporting serious adverse events

In the case of occurrence of an SAE, the Investigator/sub-Investigator must immediately:

- ENTER (within 24 hours) the information related to the SAE in the appropriate screens of the e-CRF; the system will automatically send a notification to the Sponsor after approval of the Investigator/sub-Investigator within the e-CRF or after standard delay.

- SEND (within 24 hours, preferably by fax or e-mail) the signed and dated corresponding page(s) from the CRF to the representative of the monitoring team whose name, fax number, and e-mail address appear in the clinical trial protocol. Care must be taken to ensure that the patient's identify is protected and the Patient's identifiers in the study are properly mentioned on any copy of a source document provided to the Sponsor. For laboratory results, include the laboratory normal ranges.
- ATTACH a clear photocopy of all examinations carried out and the dates on which these examinations were performed. Care should be taken to ensure that the patient's identity is protected and the patient's identifiers in the clinical trial are properly mentioned on any copy of a source document provided to the Sponsor. For laboratory results, include the laboratory normal ranges.
- All further data updates should be recorded in the e-CRF as appropriate, and further documentation as well as additional information (for laboratory data, concomitant medications, patient status, etc) should be sent (by fax or e-mail) to the monitoring team within 24 hours of knowledge of the SAE. In addition, every effort should be made to further document any SAE that is fatal or life-threatening within a week (7 days) of the initial notification.
- A back-up plan (using a paper CRF process) will be used when the e-CRF system does not work.
- REPORT to head of the study site by document immediately.

Any SAE brought to the attention of the Investigator at any time after the end of study for the patient and considered by Investigator to be caused by the IMP with a reasonable possibility, should be reported to the Sponsor.

